7.5.4 Immunogenicity Testing

Blood samples (approximately 6mL) will be collected at Day 1 (Pre-dose), Week 3, 6, 12 (End of Treatment) during the double-blind study period and for Weeks 26, 39 and 52 in the open label study for immunogenicity testing (total expected volume of approximately 40mL). Samples from all sites will be shipped to a central laboratory and stored for sample analysis. Instructions for sample

CONFIDENTIAL

Version Date: 31 March 2017

collection, preparation, labeling, and shipping will be provided by the laboratory. Sample testing will occur periodically dependent upon assay development and when an adequate number of samples have been received at the laboratory. The assay configuration provides for a screening and confirmatory assay. Any positive anti-drug antibody assay results from confirmatory testing will be made available once known. It is intended to follow any subjects with positive confirmatory anti-drug antibody assay results for up to 1 year from discovery to allow for reactive antibody results to return to baseline. Any subjects with positive confirmatory anti-drug antibody assay results who have completed the study or discontinued from the study for any reason, will be contacted and requested to return to the clinical study site for additional immunogenicity testing as noted previously.

7.5.5 Urine Pregnancy Test

An in-office, highly sensitive urine pregnancy test must be performed for all female subjects of child-bearing potential at Screening and the Week 12 Visit (Early Termination, or Final Visit for the double-blind study period) and again at the end of the open-label extension Week 52 Final Visit. All female subjects of childbearing potential must have a negative urine pregnancy test prior to randomization. Urine pregnancy testing should also be conducted at an unscheduled visit for any female who is suspected of being pregnant. Any female who becomes pregnant should be withdrawn from the study and followed to term. The CRO/Sponsor must be notified of any pregnancy that occurs while on therapy. In the event of pregnancy, the site will complete a pregnancy report form to capture the pregnancy outcome.

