7.2 SELECTION OF STUDY POPULATION

7.2.1 Inclusion Criteria

Subjects must meet each of the following criteria to be considered eligible for entry into the study:

1. Subjects who provided written informed consent to participate in the study.
2. Healthy, male and non-pregnant female subjects, 18 years of age or older.
3. A diagnosis of papulopustular rosacea with ≥ 30 inflammatory facial lesions (papules, pustules) at Baseline. Subjects must have no more than 2 nodular lesions, at Baseline.
4. Subjects with the presence of telangiectasia at Baseline.
5. Subjects with an erythema score of at least 2 on the Investigator Assessment of Erythema (IAE) scale at Baseline.
6. Subjects with a grade 4 (severe rosacea) on the 5-point Investigators Global Assessment (IGA) scale at Baseline.
7. Non-nursing, female subjects of child bearing potential, who are using a highly effective form of birth control or females not of childbearing potential due to menopause (must be postmenopausal for at least one year).
 - Highly effective methods of birth control are defined as those, alone or in combination, that result in a low failure rate (i.e. less than 1% per year) when used consistently and correctly. Forms of birth control include: Oral (birth control pills), Intravaginal: (e.g. NuvaRing®), Implantable (e.g. Norplant®), injectable (e.g. Depo-Provera®) or transdermal (e.g. Ortho Evra®) contraception; intrauterine device (IUD); double-barrier (diaphragm or condom with spermicidal gel or foam); for two months prior to study enrollment (see exclusion criteria #6) or a vasectomized partner or true abstinence (in line with preferred and usual lifestyle of subject) with an acceptable form of birth control should the subject become sexually active.

CONFIDENTIAL

Version Date: 31 March 2017

Periodic abstinence (e.g., calendar, ovulation, symptothermal, post-ovulation methods) and withdrawal are not acceptable methods of contraception. All female subjects of child bearing potential must undergo an in-office, highly sensitive urine pregnancy test, with a negative result, prior to being randomized to receive study drug. In addition, women of childbearing potential must agree to have a highly sensitive urine pregnancy test at the end of the study.

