9. Subjects who have not undergone the specified washout period(s) for the following systemic treatments or subjects who require the concomitant use of any of the following systemic treatments:

Product	Washout Period (Prior to Baseline/First Dose)
▪ Antibiotics	4 weeks
▪ Corticosteroids	4 weeks
▪ Retinoids	12 weeks

10. Female subjects who are pregnant, nursing, or planning a pregnancy within the study period.
11. Subjects who have a beard, or excessive facial hair. A moustache will be allowed, if in the investigator's judgment it does not impair the assessment of rosacea.
12. Subjects using an investigational drug within 30 days of the Baseline Visit or who are currently participating in an investigational study. Use of an investigational drug/device and/or participation in another investigational study is prohibited during this study.
13. Subjects who currently abuse alcohol or drugs or who have a history of chronic alcohol or drug abuse with in the past year.
14. Subjects who have a chronic medical condition that may require the use of a prohibited medication to treat new symptoms or exacerbations, for example, rheumatoid arthritis.

CONFIDENTIAL

Version Date: 31 March 2017

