7.3 CONDUCT OF STUDY

7.3.1 Table of Study Procedures

Procedures	Screening (Within 30 days of Baseline)	Double-Blind (DB) Study Period			Open-Label Extension Study Period	
		Baseline/ Day 1 (prior to study drug application)	Interim Visits: Weeks 1, 3, 6 and 9 (± 3 days)	Final DB Visit/ET: Week 12 (± 3 days)	Study Week 16, 26 and 39 (± 14 days)	Final Open-Label Study Visit/ET ⁴ Week 52 (± 14 days)
Informed Consent	X					
Demographics, Medical and Rosacea History	X	X				
Previous Medications	X					
Concomitant Therapy/Medication Review	X	X	X	X	X	X
Limited Physical Exam	X			X		X
Vital Signs	X		X (week 6 only)	X		X
Blood collection for clinical laboratory testing	X			X		X
Blood collection for immunogenicity testing		X	X (week 3 & 6)	X	X (except Week 16)	X
Urine Pregnancy Test, if applicable	X			X		X
Investigators Global Assessment (IGA)	X	X	X	X	X	X
Investigators Assessment of Erythema (IAE)	X	X	X	X		
Other Signs and Symptoms Assessment	X	X	X	X		
Inflammatory Lesion Counts	X	X	X	X	X (week 26)	X
Inclusion/Exclusion Criteria	X	X				
Randomization		X				
Dispense Study Drug		X	X ¹	X Open-label	X	
Dispense Diary		X	X	X Open-label	X	
Drug Accountability / diary review / compliance check, and Collection of Drug and diary			X	X	X	X
Instruct on Treatment Application		X		X Open-label		
Apply Study Drug		X ²	X	X	X	X
Adverse Event Assessment		X ³	X	X	X	X

¹ Study drug will not be dispensed at the Week 1 visit.

² The first application of study drug will be performed at the study center.

³ Adverse event assessment during the Baseline visit will be performed following the first application of study drug.

⁴ The end of the study will be the date that the last study subject completes the last visit for the study.

CONFIDENTIAL

Version Date: 31 March 2017

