7.3.2.1 Screening Visit

The following procedures will be performed during the Screening visit:

- Obtain subject's written informed consent prior to initiating any study procedures, including instructing the subject to discontinue use of medication that requires a washout (see Section 7.6.11.1). Provide subject with a copy of signed and dated consent form. Document subject's informed consent in the subject's medical record.
- Screen the potential subject according to the study inclusion/exclusion criteria.
- Schedule the Baseline/Day 1 visit to occur after the results of the laboratory safety testing are received and any required washout period is completed.
- Record Demographic information including age, sex, race, ethnicity and Fitzpatrick skin type (Appendix B)
- Record medical history. Include information on subject's history of rosacea and any previous therapies, including:
 - The approximate date of physician's diagnosis of rosacea;
 - The subject reported signs and symptoms of rosacea,
 - How often they experience these symptoms?
 - Whether symptoms are continuous or occasional?
 - What, if anything, appears to trigger or worsen these symptoms?
 - Sunlight
 - Stress
 - Alcohol
 - Exercise
 - Hot and cold temperatures
 - Spicy food
 - Previous rosacea therapies within the previous 5 years;
- Review and record concomitant medications used in the last 30 days
- Assess whether the subject will require a washout period
- Perform a limited Physical Exam (refer to Section 7.5.2) with vital signs, height and weight measurements.
- Obtain a blood sample for hematology and chemistry analysis
- Perform an in-office urine pregnancy test on all females of childbearing potential.
- Perform the Investigators Global Assessment (IGA) of rosacea, the Investigators Assessment of Erythema (IAE) and Other Signs and Symptoms Assessment before performing the lesion count (refer to Section 7.4.1, 7.4.2, and 7.4.3). **It is important that the same evaluator performs the**

CONFIDENTIAL

Version Date: 31 March 2017

evaluations for the same subject at each visit, however it may not be feasible in all instances. Every effort should be made to maintain consistency of the evaluator for each subject.

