7.3.2.2 Baseline Visit (to be scheduled within 30 days of Screening)

- Review the study inclusion/exclusion criteria to confirm eligibility, including review of the laboratory results for any clinically significant findings that would exclude the subject from eligibility for the study.
- Review any changes since the first visit in concomitant medications/therapies and the subject's health.
- Perform the Investigators Global Assessment (IGA) of rosacea, the Investigators Assessment of Erythema (IAE) and Other Signs and Symptoms Assessment before performing the lesion count (refer to Section 7.4.1, 7.4.2, and 7.4.3). **Every effort should be made to maintain consistency of the evaluator for each subject.**
- Perform the inflammatory lesion count (papules and pustules) (refer to Section 7.4.4). **Every effort should be made to maintain consistency of the evaluator for each subject.**
- If the subject has fulfilled the eligibility requirements, as stated in the inclusion/exclusion criteria, randomize the subject to treatment according to randomization instructions using the eDC system to access the Interactive Web Response System (IWRS). The eDC/IWRS system will generate the kit number assigned to the randomized subject for the duration of the study. The subject's assigned kit number should match the kit number on all drug treatment supplies dispensed to the subject. Record the subject number on the kit that is assigned to that subject.
- Record the assigned kit number and the subject number on the source document.
- Obtain the Pre-Dose blood sample for immunogenicity testing prior to the first application of study gel.
- First Treatment Application –
 - Weigh a tube that is designated to be dispensed to the subject prior to the subject applying their first dose of study medication. The tube should be weighed with the cap on as outlined in Section 7.6.9.
 - Give the subject a copy of the treatment application instructions (see Appendix A) and allow the subject to take time to read them. Provide instruction to the subject on the daily application of study drug and confirm the subjects understanding of the instructions.
 - Record the Subject # and date of dispensing on the tube label and dispense the tube to the subject.

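### The only scheduled pregnancy test before randomization is at Screening, up to 30 days before the first application, and none is scheduled at Baseline

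*Protocol*

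**What the plan says.** Exclusion 10 in Protocol 7.2.2 bars "Female subjects who are pregnant, nursing, or planning a pregnancy within the study period". Inclusion 7 in 7.2.1 calls for a "highly sensitive urine pregnancy test, with a negative result, prior to being randomized to receive study drug", and 7.5.5 repeats the requirement: "All female subjects of childbearing potential must have a negative urine pregnancy test prior to randomization". None of these says how recent the result must be.

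The test schedule is the same wherever it appears:

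- Section 7.5.5 has the test "performed for all female subjects of child-bearing potential at Screening and the Week 12 Visit", and again at the Week 52 final visit.
- In the 7.3.1 table, the row "Urine Pregnancy Test, if applicable" is marked under Screening, the final double-blind visit and the final open-label visit. It is blank under Baseline/Day 1.
- The Screening list in 7.3.2.1 carries the item "Perform an in-office urine pregnancy test on all females of childbearing potential". The Week 12 list (7.3.2.4) and the Week 52 list (7.3.2.6) have matching items.

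The Baseline list in 7.3.2.2 opens with the item "Review the study inclusion/exclusion criteria to confirm eligibility, including review of the laboratory results for any clinically significant findings". It then covers randomization and the supervised first application, and contains no pregnancy test. Baseline is to fall no more than 30 days after Screening. Under 7.3.2.1 it also waits for the safety laboratory results and the end of any washout.

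Section 7.5.5 adds a test at an unscheduled visit when pregnancy is suspected, and withdrawal with follow-up to term if pregnancy occurs. The SAP does not deal with pregnancy testing.

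**The concern.** Pregnancy status can change between Screening and Baseline, just as disease severity can. The protocol measures severity again at Baseline: IGA, erythema score, telangiectasia and lesion count are all repeated before randomization. Pregnancy is not re-tested.

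A woman who conceives after Screening, or whose pregnancy was too recent to show then, can therefore have passed every scheduled test. She would be randomized and treated although Exclusion 10 bars her. Unless pregnancy is suspected in the meantime, the next scheduled test comes at the end of the 12-week double-blind period. What is at stake is subject safety and the enforcement of one of the protocol's own eligibility rules.

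**Working it through.** The plan gives no figure of its own to reproduce. The check is a comparison of sections, followed by arithmetic on visit intervals and a rough expected count.

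**1. Is the missing Baseline test real?** Section 7.5.5, the 7.3.1 table and the visit lists in 7.3.2.1, 7.3.2.2, 7.3.2.4 and 7.3.2.6 all agree: Screening, Week 12 and Week 52 (or early termination). A table damaged in reading would not explain agreement across running text and lists.

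**2. Could the Screening test fall on the day of the first application?** Not as planned, because 7.3.2.1 puts Baseline after receipt of the laboratory results. Exclusions 8 and 9 add washouts. If one starts at Screening, a 2-week product makes the result at least 2 × 7 = 14 days old at Baseline, and a 4-week product at least 4 × 7 = 28 days old. The upper limit in 7.3.1 and 7.3.2.2 is 30 days.

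**3. Longest planned interval between the two tests around the first application.**

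- Screening to Baseline: up to 30 days
- Baseline to Week 12: 12 × 7 = 84 days
- Week 12 visit window: up to 3 days late
- Total: 30 + 84 + 3 = 117 days

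**4. Expected conceptions between Screening and Baseline.** Inclusion 7 describes highly effective contraception as failing in less than 1% of users per year when used consistently and correctly. Over 30 days the bound per woman is 0.01 × 30/365 = 0.00082. The number of women of childbearing potential is not stated, so a range is assumed:

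| Women of childbearing potential | Expected conceptions in 30 days |
|---|---|
| 100 (assumed) | fewer than 100 × 0.01 × 30/365 = 0.08 |
| 250 (assumed) | fewer than 250 × 0.01 × 30/365 = 0.21 |
| 450 (every planned subject, an extreme) | fewer than 450 × 0.01 × 30/365 = 0.37 |

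These bounds hold for correct use of contraception and scale in proportion if the true failure rate is higher; the documents give no rate for imperfect use. They also leave out pregnancies that began before Screening but were too early to detect then.

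**The case against.** The strongest reply is that nothing in the protocol is breached. Both statements of the requirement ask only for a negative result before randomization, a Screening test supplies one, and no section sets a maximum age for it. That stands: this is a gap in the schedule and not a contradiction.

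It is also fair to say that pregnancy is not ignored at Baseline. The site reviews the criteria again, including Exclusion 10, and asks about changes in health. Inclusion 7 requires highly effective contraception, and suspicion of pregnancy triggers a test. Protocol 5.1 adds that no systemic absorption was detected in the maximum-use study. These are real but partial safeguards. None is a scheduled test near the first application, and an unrecognised early pregnancy would raise no suspicion. So the accurate statement is that status is not re-tested, rather than not checked.

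Three stronger readings are tempting, and none should be drawn.

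- A reader might infer that a subject found pregnant loses her Week 12 outcome in the ITT analysis. A woman found by the Week 12 test is at a visit where the IGA and lesion count are also collected (7.3.2.4). One withdrawn earlier is to have the Week 12 procedures done (7.2.3). SAP 6.1 assigns that visit by study day, and SAP 6.2 imputes what is missing.
- A reader might infer that a 12-week washout lets the Screening result grow older than 30 days. Both 7.3.1 and 7.3.2.2 cap the interval at 30 days, and nothing permits Baseline to slip past it. Whether such a washout fits that window is a separate question.
- A reader might infer that a Baseline test would close the gap. It would narrow it, since a pregnancy too early to detect tests negative on Day 1 as well.

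**Conclusion.** The point holds as a minor one about subject safety and eligibility. A site following the protocol exactly can randomize and treat a woman whom Exclusion 10 bars, because her qualifying test may be up to 30 days old and the next scheduled one may be 117 days after it. The likely number of cases is well below one: under about 0.08 to 0.21 across the trial, on an assumed 100 to 250 women of childbearing potential and correct use of contraception. No sample size, power, error rate or planned analysis changes. The reason to act is that the consequence for an individual would be serious while the remedy is nearly free.

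**What to change.** Reconcile Exclusion 10, Inclusion 7 and 7.5.5 with the 7.3.1 table and the 7.3.2.2 list, so that the negative result that qualifies a subject is current at randomization, and state in Inclusion 7 which result that is. The simplest way to align them is to schedule the in-office urine test already in the protocol at Baseline, before randomization, either moved from Screening or repeated. How current the result must be is for the sponsor to decide and write down.

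The edit is one table entry and a sentence or two. If the test is repeated, the cost is at most one more urine test per woman of childbearing potential. If it is moved, no test is added, but some screen failures would be found later, after washout has begun.

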7.5.6 Adverse Event

7.5.6.1 Definition of Adverse Event

An adverse event (AE) is any unfavorable and unintended sign (including a clinically significant abnormal laboratory finding, for example), symptom, or disease temporally associated with the use of a medicinal product, whether or not considered related to the medicinal product.

Clinical signs and symptoms of rosacea: erythema, telangiectasia, burning, dryness, scaling/peeling and pruritus are considered as part of the baseline dermatological history. If a new rosacea sign or symptom or worsening of a rosacea sign or symptom is believed by the investigator to be related to the study drug and not the disease, then it should also be recorded as an AE.

At each visit, the study site personnel will question the subject about adverse events using an open question taking care not to influence the subject's answers, e.g., "Have you had any problems since your last visit?"

Any adverse event, whether or not it is related to the test products, will be reported on the source document and eCRF along with the date of onset, the severity, the relationship to the test product and the outcome. Under certain circumstances, additional information may be requested.

CONFIDENTIAL

Version Date: 31 March 2017

When an adverse event persists at the end of the study, the Investigator will ensure a follow-up of the subject until the Investigator/CRO/Sponsor agree that the event is satisfactorily resolved or that no further follow-up is required.

7.5.6.2 Severity and Relationship of Adverse Event to Study Drug

The severity of an adverse event is to be scored according to the following scale:

1	Mild	Awareness of sign or symptom, but easily tolerated
2	Moderate	Moderate Discomfort enough to cause interference with usual activity
3	Severe	Severe Incapacitation with inability to work or perform usual activity

The relationship of an adverse event to study drug is to be assessed according to the following definitions:

- Not Related – no temporal association or the cause of the event has been identified, or the drug cannot be implicated based upon available information.
- Possibly Related – temporal association, but other etiologies are likely to be the cause. However, involvement of the drug cannot be excluded, based upon available information.
- Definitely Related – established temporal or other association (e.g., re-challenge) and event is not reasonably explained by the subject's known clinical state or any other factor, based on available information.

7.5.7 Serious Adverse Event

A serious adverse event (SAE) is any adverse event (AE) or suspected adverse reaction (SAR) that, in the view of either the investigator or sponsor, results in any of the following outcomes:

- Death;
- A life-threatening adverse event or life-threatening suspected adverse reaction, (the term "life-threatening" in the definition of "serious" refers to an event or suspected adverse reaction in which in the view of either the investigator or sponsor, its occurrence places the patient or subject at immediate risk of death. It does not include an adverse event or suspected adverse reaction that, had it occurred in a more severe form, might have caused death);
- Inpatient hospitalization or prolongation of existing hospitalization;
- Persistent or significant incapacity; or substantial disruption of the ability to conduct normal life functions; or
- A congenital anomaly/birth defect.

Important medical events that may not result in death, be life-threatening, or require hospitalization may be considered serious adverse drug experience when, based upon appropriate medical judgment, they may jeopardize the patient or subject and may require medical or surgical intervention to prevent one of the outcomes listed in the serious adverse event definition above. Examples of such medical

CONFIDENTIAL

Version Date: 31 March 2017

events include allergic bronchospasm requiring intensive treatment in an emergency room or at home, blood dyscrasias or convulsions that do not result in inpatient hospitalization, or the development of drug dependency or drug abuse.

The Investigator or designee must report any SAE occurring in a subject receiving study medication to the Medical Monitor immediately (within 24 hours (1 business day) of becoming aware of the event), even if the SAE does not appear to be drug-related. This should be done by telephone and/or by sending a copy of the Serious Adverse Event form (via fax or email pdf copy) plus other supporting documentation, as required. SAE forms should be sent to:

[REDACTED]

All additional follow-up evaluations must also be reported as soon as possible. All SAEs will be followed until the CRO/Sponsor agrees that the event is satisfactorily resolved or that no further follow-up is required.

The CRO/Sponsor will be responsible for notifying the relevant authorities of any SAE according to applicable regulations. The CRO/Sponsor will also ensure that any central IRB/IEC and any other participating Investigators are notified of the SAE, as required. The PI is responsible for ensuring that their local IRB/IEC, if applicable, is notified of the SAE, as per the IRB/IEC standard operating procedures.

Serious Adverse Events must be reported immediately to the appropriate medical monitor as listed below:

Medical Monitors:

[REDACTED]

[REDACTED]

[REDACTED]

